4. DRUG USE INVESTIGATION COHORT

4.1 Number of subjects/centers

~~As per the MFDS requirements, safety information from a total of at least 600 evaluable subjects is needed for this drug use investigation. In consideration of a dropout rate of 20%, about 720 subjects in total will be enrolled over a period of 6 consecutive years.~~

According to MFDS requirement, at least 600 evaluated subjects should be recruited for each drug use investigation. Therefore, about 1440 subjects (720 for 3 years old and above and 720 between 6-35 months old) will be enrolled through the drug use investigation period in anticipation of a dropout rate of 20% but depending on the status of actual enrolment, the plan can be adjusted.

4.1.1 Recruitment at study centers

This prospective, observational drug use investigation will be conducted at multiple centers (mainly in hospitals and private clinics) in Korea ~~for a period of 6 consecutive years~~.

- Study population: Subjects aged ≥ 36 months who receive *Fluarix Tetra* as a part of routine practice at a private clinic or hospital. Only subjects to whom *Fluarix Tetra* will be prescribed is administered in routine clinical practice will be invited to participate in the drug use investigation.
- ~~Target enrolment: Around 720 subjects in total will be enrolled over a period of 6 consecutive years to meet the requirement of 600 evaluable subjects.~~

6.5.2.2. Pre-vaccination body temperature

The body (oral, axillary or tympanic) temperature of all subjects needs to be measured prior to *Fluarix Tetra* administration. The preferred route for recording temperature in this drug use investigation will be oral/axillary/tympanic **depending on the age of enrolled vaccinees**. If the subject has fever [fever is defined as temperature $\geq 37.5^{\circ}\text{C}$ (99.5°F) on oral, axillary or tympanic setting on the day of vaccination, the vaccination visit will be rescheduled.

7.1.1 Definition of an adverse event

Examples of included ~~an~~AE include :

Examples of included ~~an~~AE (Do Not include) :

7.2.1. Time period for detecting and recording adverse events, adverse drug reactions serious adverse events, and pregnancies

- An overview of the protocol-required reporting periods for AEs, ADRs, SAEs **and pregnancies** is given in

[Table 2](#).

~~Table 2 presents the reporting periods for AEs, ADRs, SAEs, and pregnancies.~~

7.3.2 Contact information for reporting serious adverse events and other events to GSK Vaccines

Contact for Reporting SAEs	
Please see the Sponsor Information Sheet for contact details.	
Back-up Contact for Reporting SAEs	
GSK Vaccines Clinical Safety & Pharmacovigilance	[contact] or [contact] email: [contact]
GSK Korea	[contact] or [name]
DreamCIS	[contact]
24/24 hours and 7/7 days availability	

10.2. Sample size consideration

According to MFDS requirement, at least 600 evaluable subjects should be recruited for each drug use investigation. Therefore, about 1440 subjects (720 vaccinees ≥ 3 years old and above and 720 vaccinees between 6-35 months old) will be enrolled through the drug use investigation period. We assume that 20% of enrolled

participants might drop out (depending on the status of actual enrolment), then the plan can be adjusted accordingly

~~According to MFDS requirement, at least 600 evaluable subjects should be recruited for the drug use investigation. Therefore, about 720 subjects will be enrolled through the drug use investigation period in anticipation of a dropout rate of 20%. Depending on the status of actual enrolment, the plan can be adjusted.~~

Table 4 presents the exact two-sided 95% CI for a sample size of 600 subjects **for each group**²⁾.

10.4.1. Sequence of analyses

Analysis will be performed bi-annually for the first two years and annually for the remaining follow-up years **for each study group (3 years old and above, and 6-35 months old children)**. (based on pre defined cut-off date for enrolment). A comprehensive analysis, pooling all years will be performed at the end of the drug use investigation. The analysis, including individual data listings, will be based on the cohort for vaccinated subjects for whom the drug use investigation conclusion page has been received at GSK before the pre-defined cut-off date. All periodic and final statistical analysis reports will be sent to the GSK VCSP and to MFDS.

11.1 Case Report Form

While completed CRFs are reviewed by a GSK Vaccines' **designated** study monitor at the study site, omissions or inconsistencies detected by subsequent in-house CRF review may necessitate clarification or correction of data or omissions or inconsistencies with documentation and approval by the physician or appropriately qualified designee. In all cases the physician remains accountable for the study data collected.

According to MFDS requirement, at least 600 evaluable subjects should be recruited for each drug use investigation. Therefore, ~~about max~~ 720 1440 subjects (720 for 3 years and above vaccinees and 720 vaccinees 6-35 months old) will be enrolled through the drug use investigation period. We assume that 20% of enrolled participants might drop out (depending on the status of actual enrolment), then the plan can be adjusted accordingly

3. STUDY DESIGN OVERVIEW

Sequential Allocation of Subject Numbers	
	Fluarix Tetra (N= 720 max 1,440 (720 vaccinees \geq 3 years old, 720 vaccinees between 6-35 months old))
Vaccination (Fluarix Tetra)	Drug Use Investigation Conclusion 21 days (Day 0 to Day 20) follow-up after vaccination with Fluarix Tetra
N: Number of subjects planned to be enrolled	

4. DRUG USE INVESTIGATION COHORT

4.1 Number of subjects/centers

According to MFDS requirement, at least 600 evaluated subjects should be recruited for each drug use investigation. Therefore, ~~about~~max 1440 subjects (720 for 3 years old and above and 720 between 6-35 months old) will be enrolled through the drug use investigation period in anticipation of a dropout rate of 20% but depending on the status of actual enrolment, the plan can be adjusted.

7.3.2 Contact information for reporting serious adverse events and other events to GSK Vaccines

Contact for Reporting SAEs, ADRs and Pregnancies	
Please see the Local PMS Contact Information for contact details.	
Back-up Contact for Reporting SAEs, ADRs and Pregnancies	
GSK Vaccines Clinical Safety & Pharmacovigilance	[contact] or [contact] email: [contact]
GSK Korea	[contact] or [name]
DreamCIS	[contact]
24/24 hours and 7/7 days availability	

7.3.3 Completion and transmission of SAE to GSK Vaccines

Facsimile (Fax) **or E-mail** transmission of the SAE Report Form is the preferred method to transmit this information to the ~~Contact for Reporting SAEs~~ the Contact for Reporting SAEs, ADRs and Pregnancies. In rare circumstances and due to failure of facsimile equipment, notification by telephone is acceptable, with a copy of the SAE Report Form sent by overnight mail. Initial notification via the telephone does not replace the need for the physician to complete and sign the SAE Report Form within 24 hours.

In the event of a death determined by the physician to be related to vaccination, sending of the fax must be accompanied by telephone call to the ~~Contact for Reporting SAEs~~ the Contact for Reporting SAEs, ADRs and Pregnancies.

7.3.4 Completion and transmission of SAE to GSK Vaccines

The physician sends ADR Report Form to the ~~GSK staff (or designee)~~ the Contact for Reporting SAEs, ADRs and Pregnancies that collects an adverse drug reaction by fax or e-mail. ~~Below are the fax number, telephone number and address of the GSK staff (or designee) collecting an adverse drug reaction.~~

7.3.5 Completion and transmission of pregnancy reports to GSK Vaccines

Once the physician becomes aware that a subject is pregnant, the physician (or designee) must complete a Pregnancy Report Form and fax **or e-mail** it to the ~~Contact for Reporting SAEs~~ the Contact for Reporting SAEs, ADRs and Pregnancies (refer to the Sponsor Information Sheet) within 2 weeks, if possible.

The Pregnancy Report Form will always be completed as thoroughly as possible with all available details and then dated and signed by the physician (or designee), if possible. Even if the physician does not have all information regarding the pregnancy, the form should still be completed and forwarded to GSK within 2 weeks, if possible. Once additional relevant information is received, the form will be updated and forwarded to GSK within 2 weeks, if possible.

In absence/dysfunction of facsimile equipment, the ~~Contact for Reporting SAEs~~ the Contact for Reporting SAEs, ADRs and Pregnancies should be notified by telephone within 2 weeks, if possible. As soon as the facsimile equipment is working again, the physician (or designee) must fax the Pregnancy Report Form to the ~~Contact for Reporting SAEs~~ the Contact for Reporting SAEs, ADRs and Pregnancies (refer to the Sponsor Information Sheet) within 2 weeks, if possible.

7.3.6 Regulatory reporting requirements for serious adverse events

The physician will promptly report all SAEs to GSK in accordance with the procedures detailed in Section 0. GSK Vaccines has a legal responsibility to promptly notify, as appropriate, both the local regulatory authority and other regulatory agencies about the safety of a product surveillance. Prompt notification of SAEs by the physician to the

~~Contact for Reporting SAEs~~ the Contact for Reporting SAEs, ADRs and Pregnancies is essential so that legal obligations and ethical responsibilities towards the safety of other subjects are met.

10.2. Sample size consideration

According to MFDS requirement, at least 600 evaluable subjects should be recruited for each drug use investigation. Therefore, ~~about~~~~max~~ 1440 subjects (720 vaccinees \geq 3 years old and above and 720 vaccinees between 6-35 months old) will be enrolled through the drug use investigation period. We assume that 20% of enrolled participants might drop out (depending on the status of actual enrolment), then the plan can be adjusted accordingly

## Revisions

DATE OF REVISION	INDICATION REVISION	REASON FOR CHANGE	AUTHOR NAME
20-OCT-2017	3.1 Safety Analysis Sets 3.2 Non-Safety Analysis Sets  6. Statistical Analysis 6.3.2 Adverse Events by Preferred Terms  6.2 Subject characteristics 6.3.1 Adverse Events by Subject Characteristics	Change the inclusion/exclusion criteria for the Analysis Sets  Add representing the preferred terms according to the proportion of AE in the local product document  Add the item for analysis	
04-NOV-2019	1.1 Study Background 1.2 Study Objective 2.1 Study Period 2.2 Number of Subjects 2.3 Study Population 2.3.1 Inclusion criteria 2.4 Study Method 3.1 Safety Analysis Sets 3.2 Non-Safety Analysis Sets 6.2 Subject characteristics	Update the extension of an age indication to include 6 to 35 months of age	
	2.4 Study Method 5.1 Safety Assessment Criteria 6.2 Subject characteristics	Wording revision according to protocol amendment	
	6. Statistical Analysis	Clarification of condition for analysis of pregnancy report and each study group / Addition of other analyses	
	6.2 Subject characteristics	Clarification of not applicable items for study group aged 6-35 months	
	6.3.1 Adverse Events by Subject Characteristics	Clarification of variables excluded from the analysis	
	6.3.3 Other Analyses	Addition of analyses as per GSK central team request	

		Last Update Date
dreamcis A TIGERMED COMPANY	CONFIDENTIAL : THIS DOCUMENT AND INFORMATION CONTAINED HEREIN IS PROPRIETARY TO COMPANY AND IS NOT TO BE DISCLOSED WITHOUT THE WRITTEN PERMISSION OF COMPANY.	10-SEP-2021

## STATISTICAL ANALYSIS PLAN(V5.0)

13-JUL-2020	6.2 Subject characteristics	Change of pediatric age range	PPD [REDACTED]
	6.3.2 Adverse Events by Preferred Terms	Change of AE coding dictionary / Clarification of analysis method 4) and 5)	
23-SEP-2021	6. Statistical Analysis 6.3.1 Adverse Events by Subject Characteristics	Addition of logistic regression analysis of occurrence of AE	PPD [REDACTED]
	6.2 Subject characteristics	Wording revision for clarity	

	CONFIDENTIAL : THIS DOCUMENT AND INFORMATION CONTAINED HEREIN IS PROPRIETARY TO COMPANY AND IS NOT TO BE DISCLOSED WITHOUT THE WRITTEN PERMISSION OF COMPANY.	Last Update Date 10-SEP-2021
STATISTICAL ANALYSIS PLAN(V5.0)		

## 1. Study Background and Study Objective

### 1.1 Study Background

Vaccination is currently the most effective means of controlling the impact of influenza in populations at risk (elderly and children). Influenza viruses circulate in humans virtually every winter in temperate regions of both hemispheres and throughout the year in tropical regions.

Currently, the strategy is to use a trivalent influenza vaccine which contains two A strains (H1N1 and H3N2) and one B strain. Since 1983, two evolutionarily distinct strains of influenza B virus coexist in the human population and since 1988 both strains are circulating in various countries worldwide [Barr, 2006]. In five of the last eight years, more influenza cases were due to the mismatched B virus than to H1N1 virus [CDC, 2010].

Data in literature suggest that children, without appropriate immunologic priming, vaccinated with a vaccine containing the recommended B-strain might not be protected against an infection with the co-circulating strain from the other B-lineage. Indeed, in a study on non-immunized (unprimed) infants, no cross-reactive antibodies were found in the sera [Levandowski, 1991].

As the two evolutionarily distinct strains of influenza B virus co-circulate and as cross-reactivity between those two lineages is low and even almost non-existing in an unprimed population, an additional B-strain antigen in the seasonal vaccine may offer a better protection [Englund, 2006; Levandowski, 1991].

GSK Vaccines has developed a QIV which contains two A-strains and two B-strains. The drug use investigation was designed to evaluate the safety of the QIV in adults and children from six months of age in Korea.

### 1.2 Study Objective

To assess the safety of GSK Vaccines' quadrivalent seasonal influenza vaccine D-QIV, Fluarix Tetra, in terms of frequency and intensity of AEs and SAEs when administered according to the local PI in adults and children from six months of age in Korea.

	CONFIDENTIAL : THIS DOCUMENT AND INFORMATION CONTAINED HEREIN IS PROPRIETARY TO COMPANY AND IS NOT TO BE DISCLOSED WITHOUT THE WRITTEN PERMISSION OF COMPANY.	Last Update Date 10-SEP-2021
STATISTICAL ANALYSIS PLAN(V5.0)		

## 2. Study Design

### 2.1 Study Period

GSK Vaccines' quadrivalent seasonal influenza vaccine D-QIV, Fluarix Tetra was registered in Korea in December 2014. As per MFDS requirements, this drug use investigation (as part of PMS) is being conducted to collect safety information on the use of Fluarix Tetra over a 6 years period.

In addition to the extension of an age indication to include 6 to 35 months of age for Fluarix Tetra, additional drug use investigation for new age group is being conducted to collect safety information on the use of Fluarix Tetra for 4 years according to the MFDS requirement.

### 2.2 Number of Subjects

According to MFDS requirement, at least 600 evaluable subjects should be recruited for each drug use investigation. Therefore, max 1440 subjects (720 vaccinees  $\geq$  3 years old and above and 720 vaccinees between 6-35 months old) will be enrolled through the drug use investigation period. We assume that 20% of enrolled participants might drop out (depending on the status of actual enrolment), then the plan can be adjusted accordingly.

### 2.3 Study Population

Subjects aged  $\geq$  6 months who receive Fluarix Tetra as a part of routine practice at a private clinic or hospital. Only subjects to whom Fluarix Tetra is administered in routine clinical practice will be invited to participate in the drug use investigation.

#### 2.3.1 Inclusion criteria

All subjects must satisfy the following criteria at drug use investigation entry:

- (1) Male or female subjects who were vaccinated with Fluarix Tetra or eligible to receive Fluarix Tetra according to the locally approved PI.

\*Note: According to current approved PI, the subjects below are included.

	CONFIDENTIAL : THIS DOCUMENT AND INFORMATION CONTAINED HEREIN IS PROPRIETARY TO COMPANY AND IS NOT TO BE DISCLOSED WITHOUT THE WRITTEN PERMISSION OF COMPANY.	Last Update Date 10-SEP-2021
STATISTICAL ANALYSIS PLAN(V5.0)		

Subjects	1st dose	Follow-up contact after 21 days	2nd dose	Follow-up contact after 21 days
Primed	•	•		
Unprimed 	•	•	•	•
Unprimed 	•	•		
Unprimed with history of Fluarix Tetra 			•	•

- Primed: adults and previously vaccinated children aged  $\geq 6$  months

- Unprimed: previously unvaccinated children aged 6 months to  $<9$  years

 Unprimed children who participate in the drug use investigation following the administration of both doses of Fluarix Tetra

 Unprimed children who participate in the drug use investigation following the administration of the first dose of Fluarix Tetra

 Unprimed children who participate in the drug use investigation following the administration of the second dose of Fluarix Tetra

- 2nd dose would be given at least 4 weeks after the 1st dose.

(2) Signed informed consent as ICF/IAF obtained from the subject/subject's parent(s)/LAR(s).

### 2.3.2 Exclusion criteria

The following criteria should be checked at the time of drug use investigation entry. If the exclusion criterion applies, the subject must not be included in the study:

(1) Those who are not eligible for vaccination with Fluarix Tetra according to the local PI.

- Hypersensitivity reaction to Fluarix Tetra
- History of hypersensitivity reaction to Influenza vaccine
- History of Guillain-Barre syndrome or other nervous abnormalities to Influenza vaccine within 6 weeks post-vaccination

(2) Those who are not eligible for vaccination with Fluarix Tetra according to the medical judgement of physician.

	CONFIDENTIAL : THIS DOCUMENT AND INFORMATION CONTAINED HEREIN IS PROPRIETARY TO COMPANY AND IS NOT TO BE DISCLOSED WITHOUT THE WRITTEN PERMISSION OF COMPANY.	Last Update Date 10-SEP-2021
STATISTICAL ANALYSIS PLAN(V5.0)		

## 2.4 Study Method

This prospective, observational drug use investigation will be conducted at multiple centers (mainly in hospitals and private clinics) in Korea.

Only subjects to whom Fluarix Tetra is administered in routine clinical practice will be invited to participate in the drug use investigation.

## 3. Analysis Sets

### 3.1 Safety Analysis Sets

The safety analysis set will include all subjects who receive Fluarix Tetra, participated in the drug use investigation and provide post vaccination safety data.

The cases below shall be excluded from safety analysis set in the following order:

- (1) Subjects who have consented prior to the contract
- (2) Subjects who have been administered prior to the contract\*
- (3) Subjects who didn't receive Fluarix Tetra within this study
- (4) Follow-up failure: Subjects for whom adverse event status (Adverse Events status is unknown or missing in CRF) could not be established
- (5) Subjects who violated inclusion/exclusion criteria (see section 2.3)
- (6) Subjects who were prescribed for other indications except indications in the local product document.

[Target Indication]

- Fluarix Tetra is indicated for active immunisation of adults and children from 6 months of age for the prevention of influenza disease caused by the influenza A virus subtypes and the influenza B virus types contained in the vaccine.

- (7) Subjects who violate the dosage

[Dosage]

- Children from 6 months and older receive 0.5 ml dose by intramuscular injection and is revaccination each year.
- For children aged < 9 years, who have not previously been vaccinated against influenza, a second dose should be given after an interval of at least 4 weeks.

	CONFIDENTIAL : THIS DOCUMENT AND INFORMATION CONTAINED HEREIN IS PROPRIETARY TO COMPANY AND IS NOT TO BE DISCLOSED WITHOUT THE WRITTEN PERMISSION OF COMPANY.	Last Update Date 10-SEP-2021
STATISTICAL ANALYSIS PLAN(V5.0)		

(8) Subjects of contraindications

[Contraindication]

- History of hypersensitivity to the active substances or to any of the excipients or to any component that may be present as traces such as eggs (ovalbumin, chicken proteins), formaldehyde, gentamicin sulphate and sodium deoxycholate
- Immunisation should be postponed in patients with febrile illness or acute infection.
- History of hypersensitivity reaction to Influenza vaccine
- History of Guillain-Barre syndrome or other nervous abnormalities to Influenza vaccine within 6 weeks post-vaccination

\* But subjects not administered the Fluarix Tetra this season shall be included from safety analysis set. In addition, subjects under age 9 years who participating in the drug use investigation with a second dose of Fluarix Tetra shall be included from safety analysis set.

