6.3.4.1. Time window for recording concomitant medication/vaccination in the CRF

All concomitant medications, with the exception of vitamins and/or dietary supplements, administered at any time during the period starting with the administration of *Fluarix Tetra* and ending 21 days (Day 0 to Day 20) after vaccination must be recorded in the CRF.

Any vaccine not foreseen in the drug use investigation protocol administered in the period beginning 21 days (Day -20 to Day 0) preceding the dose of *Fluarix Tetra* and ending 21 days (Day 0 to Day 20) after the dose of *Fluarix Tetra* must be recorded in the CRF.

Any investigational medication or vaccine administered throughout the drug use investigation (i.e. from 21 days before the first dose of the vaccine and 21 days after administration of the dose of the vaccine) must be recorded in the CRF.

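### Does the SAP's dosage-violation rule remove previously unvaccinated children under 9 who were followed after one dose only?

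*SAP*

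**What the plan says.** SAP 3.1 lists eight grounds for exclusion, introduced by "The cases below shall be excluded from safety analysis set in the following order". Ground (7) is "Subjects who violate the dosage", and SAP 3.2 repeats it as ground (5) for entry to the Non-safety set. In both places the only definition is the dosage text: a 0.5 ml intramuscular dose, and for children under 9 "who have not previously been vaccinated against influenza, a second dose should be given after an interval of at least 4 weeks".

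The entry table in SAP 2.3.1, which matches Protocol 4.2, opens with "According to current approved PI, the subjects below are included". It has four rows: primed subjects, and three kinds of unprimed child (followed for both doses, for dose 1 only, or for dose 2 only). The dose-1-only row is footnoted "Unprimed children who participate in the drug use investigation following the administration of the first dose of Fluarix Tetra".

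Protocol 10.5.2 bases the safety analysis on subjects vaccinated in line with the Korean prescribing information. It asks for one fully followed dose and disregards how many doses were given. A footnote in SAP 3.1 and 3.2 says that children under 9 who take part with a second dose belong in the safety analysis set.

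On recording, Protocol 6.3.4.1 covers vaccines "administered in the period beginning 21 days (Day -20 to Day 0) preceding the dose", and this window closes at Day 20. The sentence is limited to vaccines that the protocol does not foresee. Protocol 6.5.3.4 asks for influenza vaccination history over three previous seasons.

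**The concern.** Rule (7) is written as an exclusion but lacks a working definition. A programmer who takes the dosage text literally could class an unprimed child with one recorded dose as a violator, while another would keep the child. SAP 3.1 already excludes breaches of the entry criteria under rule (5). Rule (7) therefore acts on subjects who have passed the entry table, and the table alone does not visibly stop it.

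The data also look too short to decide the matter. A second dose falls due at Day 28 or later, whereas the recording window ends at Day 20. For a child entering with dose 2, a compliant first dose lies at Day -28 or earlier, whereas the window opens at Day -20.

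Membership of the safety analysis set is at stake. That set carries the main adverse event incidence (SAP 6.3) and the subgroup and logistic analyses (SAP 6.3.1). It also supplies the count of evaluable subjects, at least 600 per group.

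**Working it through.** **1. Which text governs each entry row**

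| Row in SAP 2.3.1 | Second-dose text applies? | What settles set membership |
|---|---|---|
| Primed | No | Not in question |
| Unprimed, both doses followed | Yes | The interval is seen in the study |
| Unprimed, dose 1 only | Yes | SAP 2.3.1, Protocol 4.2, Protocol 10.5.2 |
| Unprimed, dose 2 only | Yes | Entry table, and footnote in SAP 3.1 and 3.2 |

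The second-dose text concerns three of four rows. Each has a passage pointing to inclusion or data that show the interval.

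**2. Can an absent second dose breach the dosage text?** The text sets a minimum interval of 4 × 7 = 28 days and no maximum. Follow-up after a dose runs from Day 0 to Day 20, which is 20 − 0 + 1 = 21 days and matches the protocol's figure. A dose-1-only child is scheduled to conclude 28 − 20 = 8 days before a second dose could comply. At that point its absence cannot be a violation. With no latest date in the text, an unrecorded dose does not become one at a later data cut-off.

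**3. Do the recording windows miss the relevant dose?** The arithmetic is right: 28 − 20 = 8 days after dose 1, and −20 − (−28) = 8 days before dose 2. It does not bear on the question, because the Day -20 to Day 20 rule applies to unforeseen vaccines. Protocol 3 and 4.2 name a second Fluarix Tetra dose, so it is foreseen. Table 1 of the protocol requires vaccination information in the case report form. SAP 6.2 reports the Fluarix Tetra dose separately for subjects under 9 in the 3-years-and-above group. The third unprimed row is defined by a history of Fluarix Tetra, so the earlier dose has to be established at entry.

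**4. Does the three-season history misclassify priming?** Assume one season a year and vaccination possible from 6 months of age. A child aged *a* completed years then has *a* − 1 to *a* earlier seasons, of which three are recorded.

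- Age 3: 2 to 3 seasons, so none unrecorded.
- Age 4: 3 to 4 seasons, so 0 to 1 unrecorded.
- Age 8: 7 to 8 seasons, so 4 to 5 unrecorded.

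The whole 6-35-month group is unaffected. For older children, neither document says this history decides priming for rule (7). Protocol 10.5.1 uses it as a descriptive baseline item.

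**5. Size under the strict reading (illustration only).** The documents give no share of dose-1-only children. Assume 720 enrolled in a group and 10% drop-out, so 720 × 0.90 = 648 evaluable if these children stay. If they are removed:

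| Assumed share | Evaluable |
|---|---|
| 5% | 648 × 0.95 = 616 |
| 10% | 648 × 0.90 = 583 |
| 20% | 648 × 0.80 = 518 |

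The strict reading would matter if someone adopted it, but it conflicts with Protocol 10.5.2 and the entry table.

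**The case for a change.** The strongest case for a change is that each reassurance has a weak spot. Protocol 10.5.2 disregards the number of doses but, in the same sentence, requires vaccination according to the Korean prescribing information, which is what rule (7) tests. The SAP does not carry the dose-number phrase over. Its footnote hangs on rule (2), on administration before the contract, and is silent on dose-1-only children. Because reports are cut at successive dates (Protocol 10.4.1), the same child could be classed differently from one report to the next.

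What stands is that the SAP does not define a dosage violation for this situation. The rest does not lead to exclusion. The entry table itself declares the dose-1-only row consistent with the prescribing information, so that condition in Protocol 10.5.2 does not count against these children. The stated order of the rules is most naturally a way of assigning one reason to each excluded subject. It does not show that rule (7) overrides a row the SAP has just admitted. Rule (7) still has departures to act on, such as a different volume or route, or a recorded interval shorter than 4 weeks.

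The case report form is not among the documents. It therefore cannot be shown that the dose data are missing, nor that they are complete.

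**Conclusion.** No change to the plan follows. The wording gap in SAP 3.1(7) and 3.2(5) is real, but the surrounding text fills it in one direction: previously unvaccinated children followed after one dose stay in the safety analysis set, and so do those who enter with the second dose. The argument that the recording windows fall 8 days short does not hold for a dose that the protocol foresees. The argument from the three-season history rests on a use of that history which neither document states.

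No bias, direction of error or loss of evaluable subjects has been shown. A child who was nevertheless moved would leave the main incidence figures, but SAP 6.3.2, item 3, would still tabulate the events by preferred term with exact intervals. Protocol 10.4.2 describes the investigation as descriptive. A clarifying sentence on set membership would be harmless but optional.

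This conclusion assumes that analysts read rule (7) together with SAP 2.3.1 and Protocol 10.5.2, and that they do not treat an unrecorded second dose as evidence of a violation. It concerns analysis-set membership only and takes no view on the vaccination schedule.
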